3.3. STUDY INTERVENTION

The study intervention is an intravenous infusion of milrinone (***only FDA approved milrinone products will be used in this study***) or placebo (**D5W**).

3.4. BLINDING/MASKING

The intervention will be blinded by the study pharmacist at each center. Infants, parents, care-givers will not be aware of the treatment assignment.

Accidental unmasking: if the identity of the study drug is accidentally revealed to the research or the clinical team, data collection and analysis will continue as previously planned and a protocol violation will be documented.

Intentional unmasking: if the neonatal/surgical attending requests unmasking based on the presence of a serious adverse event, he/she will be informed that the study drug may be

immediately stopped. The request for unmasking will be forwarded to the site PI, study PI and discussed with the NICHD-NRN director. If approved, the study pharmacist will be directed to reveal the identity of the study drug to the attending physician only and not the research team. If the neonatal/surgical attending requests unmasking based on a positive effect of the study drug, he/she will be informed that after the completion of study drug therapy, the clinical team may initiate open-label milrinone.

3.5. POTENTIAL RISKS AND BENEFITS TO SUBJECTS

Infants with CDH represent a high-risk population with mortality ranging from 30 to 40%. Additional risks from the use of IV milrinone include systemic hypotension, intracranial hemorrhage (reported in critically ill neonates with PPHN) and arrhythmias (reported in adults). The anticipated benefit is improvement in oxygenation and reduced need for ECMO.

Systemic hypotension is commonly seen in patients with CDH. In recent studies 80-90% of patients with CDH required treatment with vasoactive medications. (Snoek, Capolupo et al. 2016) Patients will be closely monitored for systemic hypotension due to its association with increased right –to-left shunting and hypoxemia. Study drug will be discontinued in the presence of 'severe' or 'life-threatening' systemic hypotension as outlined in the MOP that cannot be explained by other causes (such as sepsis or pneumothorax) and described below.

- a. Severe hypotension:
 - decrement in mean BP > 20 to 30 mmHg compared to the most recent value during the period prior to study drug or at baseline OR
 - receiving extensive volume therapy (40 to 80 ml/kg during a 24-hour period of the study monitoring period: onset of study drug to 24 hours after discontinuation of study drug) OR
 - escalation of vasoactive inotrope score by 20 to 30 compared to the score at baseline
- b. Life-threatening hypotension:
 - Decrease in mean BP > 30 mmHg compared to the most recent value during the period prior to study drug or at baseline OR
 - receiving volume therapy (> 80 ml/kg during a 24-hour period of the study monitoring period: onset of study drug to 24 hours after discontinuation of study drug) OR
 - escalation of vasoactive inotrope score by > 30 compared to the score at baseline)

(i) Vasoactive inotrope score calculation (vasoactive inotrope score = dopamine dose ($\mu\text{g}/\text{kg}/\text{min}$) + dobutamine dose ($\mu\text{g}/\text{kg}/\text{min}$) + epinephrine dose ($\mu\text{g}/\text{kg}/\text{min} \times 100$) + norepinephrine dose ($\mu\text{g}/\text{kg}/\text{min} \times 100$) + phenylephrine dose ($\mu\text{g}/\text{kg}/\text{min} \times 100$) + vasopressin dose ($\text{U}/\text{kg}/\text{min} \times 10000$) (Gaies, Gurney et al. 2010)

Intracranial hemorrhage has been reported in 2 patients with milrinone use in one case series. Subjects in the study will be closely monitored for intracranial hemorrhage with a first head ultrasound and a repeat ultrasound after completion of the study drug infusion. Study drug is discontinued if a 'severe' or 'life-threatening' intracranial bleed/echodensity as defined in the MOP and as described below.

- a. Severe intracranial bleed: unilateral or bilateral blood/echodensity filling the ventricle(s) resulting in distension without parenchymal bleeding and without a midline shift.
- b. Life-threatening intracranial bleed: Parenchymal hemorrhage/echodensity (including cerebellar hemorrhage) and / or any bleed/ echodensity associated with a midline shift.

Extracranial hemorrhage has not been reported in neonates with PPHN receiving milrinone. However, the study-drug should be discontinued in the presence of 'severe' or 'life-threatening' extracranial bleed (that cannot be attributed to other factors such as trauma, surgery etc,) as outlined in the MOP and described below:

- a. Severe category:
 - pulmonary or GI or other forms of extracranial bleed requiring $>15-30$ ml/kg PRBC transfusion during the study monitoring period: (onset of study drug to 24 hours after discontinuation of study drug) OR
 - associated with a 5 to 10 mm Hg decrease in mean blood pressure from the time prior to the onset of bleeding
- b. Life-threatening category: pulmonary or GI or other forms of extracranial bleed requiring PRBC transfusions (total volume of PRBC > 30 ml/kg during the study monitoring period: onset of study drug to 24 hours after discontinuation of study drug) OR associated with > 10 mm Hg decrease in mean blood pressure from the time prior to onset of bleeding.

Milrinone does not directly induce renal dysfunction. However, renal dysfunction can prolong the half-life of milrinone. New-onset renal dysfunction of 'severe' or 'life-threatening' category as outlined in the MOP) are indications for discontinuation of study-drug.

- a. Severe renal dysfunction: Serum creatinine $> 2 \text{ mg/dL}$ but $\leq 3 \text{ mg/dL}$ OR increase by 0.5 to 1 mg/dL from the most recent value during the period prior to study drug or at baseline
- b. Life-threatening renal dysfunction: Serum creatinine $> 3 \text{ mg/dL}$ OR increase by $> 1 \text{ mg/dL}$ compared to the most recent value during the period prior to study drug or at baseline

Milrinone use has been associated with arrhythmias in adults. Arrhythmias have not been reported in the neonatal population in the absence of cardiac disease or surgery. However, if 'severe' or 'life-threatening' arrhythmias (as described in the MOP) are noted after the use of milrinone and other causes (such as electrolyte disturbances or presence of a central line in the right atrium) are ruled out, the study drug should be discontinued.

- a. Severe arrhythmia:
 - i. rhythm abnormality including bradycardia (heart rate $\leq 70/\text{min}$) or tachycardia (heart rate ≥ 220 but $\leq 300/\text{min}$) OR
 - ii. arrhythmia associated with a 5 to 10 mm Hg decrease in mean blood pressure from the time prior to the onset of arrhythmia OR
 - iii. therapy with anti-arrhythmic medications, AND
 - iv. No use of pacing, cardioversion or defibrillation.
- b. Life-threatening arrhythmia:
 - i. rhythm abnormality – tachyarrhythmia with heart rate $> 300/\text{min}$ OR
 - ii. treated with pacing, cardioversion or defibrillation OR
 - iii. arrhythmia associated with a $> 10 \text{ mm Hg}$ decrease in mean blood pressure from the time prior to the onset of arrhythmia

Note: Respiratory deterioration (as reported on the toxicity table in the MOP) is common in the natural history of CDH and should not be a reason for discontinuing the study drug.

SECTION 4. METHODS

4.1. STUDY POPULATION

Infants with an antenatal or postnatal diagnosis of CDH will constitute the study population. Infants of all ethnicities and both sexes will be included. **Stratification** based on the severity of respiratory failure ($\text{PaO}_2/\text{FiO}_2 - \text{PaCO}_2$) will be performed. If the $(\text{PaO}_2/\text{FiO}_2 - \text{PaCO}_2)$ is ≥ 0 , subjects are stratified as moderate hypoxic respiratory failure (HRF) and if < 0 , as severe HRF. If no arterial blood gas is available prior to randomization, an OSI of 5 to 10 is considered “moderate” HRF and > 10 is considered “severe” HRF.

4.1.1. Inclusion Criteria

Infants are eligible if they meet all of the following criteria:

- (i) ≥ 36 0/7 weeks PMA by best obstetric estimate AND birth weight of ≥ 2000 g
- (ii) postnatal age ≤ 7 days (168 hours of age), including post-operative infants following CDH repair with HRF within this postnatal age,
- (iii) invasive mechanical ventilation (defined as ventilation with an endotracheal tube) and
- (iv) one arterial blood gas with an OI ≥ 10 (after tracheal tube obstruction, pneumothorax and other easily resolvable mechanical causes for increased OI are ruled out) on the most recent arterial blood gas within 12 hours prior to the time of randomization.
- (v) if an arterial blood gas is not available at the time of randomization, a preductal OSI of ≥ 5 can be used as an inclusion criterion instead of OI ≥ 10 ; (the OSI should be based on the most recent preductal pulse oximetry recording and must be within 12 hours of randomization)
- (vi) postnatal blood gas with $\text{PCO}_2 \leq 80$ mmHg (arterial, capillary or venous blood gas) on the most recent blood gas sample obtained within 12 hours prior to randomization

Note: Criteria (iv) to (vi) must be met at the most recent analysis within 12 hours prior to randomization.

4.1.2. Exclusion Criteria

Infants are ineligible if they meet any of the following criteria:

- known hypertrophic cardiomyopathy
 - Note 1: infants of diabetic mothers with asymmetric septal hypertrophy can be included as long as there is no evidence of obstruction to left ventricular outflow tract on echocardiogram,

- Note 2: infants with other acyanotic congenital heart disease (CHD) and CDH may be included in the study and will be a predetermined subgroup for analysis)
- cyanotic CHD – transposition of great arteries (TGA), total anomalous pulmonary venous return (TAPVR), partial anomalous pulmonary venous return (PAPVR), truncus arteriosus (TA), tetralogy of Fallot (TOF), single ventricle physiology – hypoplastic left heart syndrome (HLHS), tricuspid atresia, critical pulmonic stenosis or atresia etc.,
- enrolled in conflicting clinical trials (such as a randomized controlled blinded trial of another pulmonary vasodilator therapy); Note: mothers enrolled in fetal tracheal occlusion studies such as FETO may be enrolled if permitted by investigators of the fetal tracheal occlusion study; More information about FETO can be found at <http://www.chop.edu/centers-programs/center-fetal-diagnosis-and-treatment/fetoscopic-endoluminal-tracheal-occlusion-feto> or <http://childrens.memorialhermann.org/FETO-trial/> [FETO refers to fetoscopic endoluminal tracheal occlusion and involves occlusion of fetal trachea with a balloon device at mid-gestation and subsequent removal in later gestation]
- infants with bilateral CDH
 - Note 3: infants with anterior and central defects are included in the study
- associated abnormalities of the trachea or esophagus (trachea-esophageal fistula, esophageal atresia, laryngeal web, tracheal agenesis)
- renal dysfunction (with serum creatinine > 2 mg/dL not due to maternal factors) or oligohydramnios associated with renal dysfunction at randomization; renal dysfunction may be secondary to renal anomalies or medical conditions such as acute tubular necrosis
- systemic hypotension (mean blood pressure < 35 mm Hg for at least 2 h with a vasoactive inotrope score of > 30)
- decision is made to provide comfort/ palliative care and not full treatment
- Known intracranial bleed (including the following descriptions on the cranial ultrasound)
 - Parenchymal hemorrhage – including blood in the cerebral parenchyma, cerebellar parenchyma or basal ganglia
 - Blood/echodensity in the ventricle with distension of the ventricle
 - Midline shift secondary to mass effect from an intracranial hemorrhage
- thrombocytopenia (platelet count < 80,000/mm³) despite blood product administration on the most recent blood draw prior to randomization
- coagulopathy (PT INR > 1.7) despite blood product administration on the most recent blood draw (if checked – there is no reason to check PT for the purpose of this study)
- aneuploidy associated with short life span (such as trisomy 13 or 18) will not be included in the study (infants with trisomy 21 can be included in the study)

- use of milrinone infusion prior to randomization (the use of other inhaled pulmonary vasodilators such as iNO, inhaled epoprosternal, inhaled Treprostinal, inhaled PGE1 and oral such as endothelin receptor antagonists is permitted – Note: it is unlikely to be on oral pulmonary vasodilators early in the course of CDH)
- ongoing therapy with parenteral (intravenous or subcutaneous) pulmonary vasodilators such as IV/SQ prostacyclin analogs (Epoprostenol – Flolan® or Treprostinal – Remodulin®) or IV phosphodiesterase 5 inhibitors (sildenafil – Revatio®) at the time of randomization. Administration of IPGE1 is not an exclusion criteria. In addition, initiation of therapy with these two classes of parenteral medications (except IPGE1) during the first 24 hours of study drug initiation is not permitted and will be considered a protocol deviation. The risk of systemic hypotension is high during the first 24 hours of study-drug (milrinone) infusion and hence parenteral administration of other pulmonary vasodilators is avoided to minimize risk of hypotension.
- Subjects already on ECMO or patients who are being actively considered for ECMO by the neonatal or surgical team
- Infants with hypoxic-ischemic encephalopathy (HIE) undergoing therapeutic hypothermia
- attending (neonatal, critical care or surgical) refusal for participation in the trial (including concern about presence of hemodynamic instability)

Note:

1. A clotting profile evaluation is not required prior to enrollment. However, a cranial ultrasound (covered by the study budget) must be obtained either prior to initiation of study drug or within 4 hours of initiation of study drug. Not obtaining a cranial ultrasound within this time period will be considered a protocol deviation.
2. One complete blood count (CBC) with a platelet count of $> 80,000/\text{mm}^3$ on the most recent evaluation prior to enrollment is required for randomization. This CBC may be drawn after one or multiple platelet transfusions.
3. The use of therapies such as sedation, analgesia, paralysis, surfactant, high frequency ventilation, iNO, pressors, inhaled prostaglandins (including PGE₁ and prostacyclin) and steroids are permitted at the discretion of the clinical team (and/or based on written center guidelines – a copy of each center's guidelines, if available, will be collected prior to enrollment).
4. Infants with CDH as part of a congenital syndrome that does not cause cardiopulmonary or renal compromise (e.g., rib cage anomalies, renal dysplasia) can be included in the study. Infants with trisomy 21 and CDH without cyanotic heart disease or kidney disease affecting renal function may be included in this trial.

5. A baseline echocardiogram (if ordered for clinical indications) prior to initiation of study drug or within 6 hours of initiation of study-drug is preferred as a baseline study. However, consenting, randomization and preparation of study drug by the pharmacy may proceed without an echocardiogram. It is not necessary to wait for the “official” results of the echocardiogram to commence study drug (unless there is a high suspicion for cyanotic congenital heart disease).

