4.2. DETAILED STUDY PROCEDURES

For the purpose of the study, time period prior to study drug is defined as 12 hours prior to initiation to 30 minutes prior to initiation of study drug. Baseline is defined as the period 30 min prior to initiation of study drug. The monitoring period is defined as the period of study drug infusion and the first 24-hours following study drug cessation.

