Subject specimens: Information about blood counts, imaging and blood gases will be obtained from blood draws conducted for the purpose of clinical care. No additional blood work will be performed for the purpose of research.

Echocardiography: Data from a maximum of 4 clinical echocardiograms will be recorded. No additional echocardiograms will be performed for the purpose of this study. To estimate the secondary outcome of improvement in cardiac function and pulmonary hypertension, data from at least two echocardiograms will be obtained if available – the first echocardiogram preferably prior to initiation of the study drug. If echocardiogram is not performed prior to study drug initiation, study drug may be initiated.

If clinical echocardiograms are obtained during the study drug infusion, data from the clinical echocardiogram closest to 24 hours after study drug infusion is used to calculate the secondary outcome of change in echocardiographic findings. If a third echocardiogram is obtained close to 72 hours after initiation of study drug, data from this study will be recorded. In addition, data from any other echocardiograms obtained for clinical purposes after completion of study drug will be recorded (maximum of 4 echocardiograms).

Cranial ultrasound: As mentioned previously, an initial cranial ultrasound is obtained prior to initiation of study drug or within 4 hours of commencement of the study drug. A second cranial ultrasound is obtained preferably within 24 hours (maximum within 96 hours) of completion of the study drug. Both these cranial ultrasounds are covered by the study budget. Additional head imaging may be performed based on clinical indications but are not covered by the study budget. If the patient has a screening ultrasound that demonstrates intracranial hemorrhage

(as outlined in the exclusion criteria) prior to starting the study-drug, the patient is not randomized. In this case, only one screening cranial ultrasound is covered by the study budget.

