5.5.1 Reporting Adverse Events

There is high morbidity and mortality associated with the natural course of CDH. The following measures will be used to monitor safety of the trial based on a review of adverse events. Adverse event reporting will be handled as follows:

- (i) **Potential Adverse Events** (as defined below) will be reported on the Adverse Events form.
- (ii) Because of the nature of the study population, mild events will not be recorded as adverse events unless they are also unexpected.
- (iii) Potential adverse events listed below that are severe, life-threatening or result in death (as per the MOP toxicity table) will be entered in the electronic data capture system (EDC) within 24 hours of discovery.
- (iv) **Serious Adverse Events** will be reported on the Adverse Events form, entered in the electronic data capture system (EDC) and reported to NICHD and the NRN data center within 24 hours of discovery (via SAE Narrative)
when:
 - a) they result in death **or**
 - b) they are possibly, probably or definitely related to the intervention **or**
 - c) they are unexpected. An unexpected event is defined as an adverse event not known to be associated with the natural course of CDH or a specified side-effect of interventions in the management of CDH.
- (v) All serious adverse events that meet one of the above criteria will be reviewed by the NICHD NRN Program Scientist (as medical monitor).
- (vi) All serious events that are marked as at least possibly related to the intervention will be forwarded to the Chair of the independent NRN DSMC for any further action.

The duration of reporting adverse events would include the period of administration of the study drug and 24 hours' post-infusion. This period will cover approximately 6 half-lives of milrinone and plasma levels are expected to be undetectable by 24 hours after completion of study-drug infusion.

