5.5.2 Potential Adverse Events

The potential adverse events include:

1. Systemic hypotension
2. Abnormal cranial imaging consistent with intracranial bleed
3. Arrhythmias
4. Extracranial bleeding (especially pulmonary and gastrointestinal hemorrhage)
5. Renal dysfunction
6. Respiratory deterioration
7. Other events that are deemed severe (or worse in intensity), and either unexpected or at least possibly related to study or results in death

The data regarding serious adverse events will be reviewed after recruitment of the first 10 subjects. Subsequently, data regarding adverse events will be reviewed every 17 subjects (25% of the sample size). If DSMC is concerned about adverse events, the subjects can be unmasked for the DSMC to assess whether the event rates appear to differ between treatment arms. Should there be excess serious adverse events in one group, the committee may recommend breaking of the blinding and discontinuation of enrollment.

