5.5.3 Interim Monitoring Plan and Stopping Rules

As mentioned previously, the DSMC will meet as per the following plan. A suggested schedule may include meeting after the first 10 subjects are enrolled and at 25% (~ 17 subjects), 50% (33 subjects), 75% (~ 50 subjects) of target sample size and after completion of enrollment.

In addition to monitoring trial progress, the DSMC will also review accumulating safety data for the trial. All safety data presented to the DSMC will be blinded to treatment group, though the report may be unmasked at the DSMC's request.

The three main adverse events that require close monitoring include severe hypotension , hemorrhage (intracranial and extracranial) and arrhythmia or death due to severe hypotension or intracranial hemorrhage or arrhythmia while on study drug infusion or 24 hours after cessation of study drug infusion.

The presence of the following adverse events *possibly, probably or definitely due to the study drug* in > 20% of subjects after enrollment of 33 patients with a statistically significant difference between the treatment arm and the placebo arm can lead to a discussion at DSMC regarding cessation of the trial.

- (a) Severe hypotension is defined by a decrease in mean blood pressure > 20 to 30 mmHg compared to baseline OR receiving extensive volume therapy (>40 to 80 ml/kg during a 24 hour period of the study monitoring period OR escalation of vasoactive inotropic score by >20 to 30 compared to baseline) The study monitoring period is the time on study drug therapy and within 24 hours of completion of study drug therapy.
- (b) Life-threatening hypotension - receiving volume therapy > 80 ml/kg during a 24 hour period of the study monitoring period OR escalation of vasoactive inotropic score by > 30 compared to baseline
- (c) Severe intracranial hemorrhage (unilateral or bilateral blood/ echodensity filling the ventricle(s) resulting in distension without parenchymal bleeding and without a midline shift) while on study drug therapy and within 24 hours of completion of study drug therapy.
- (d) Life-threatening intracranial hemorrhage - Parenchymal hemorrhage/ echodensity (including cerebellar hemorrhage) and / or any bleed/ echodensity associated with a midline shift.

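### Intracranial bleeds: the scan schedule and the 24 h event window do not match, and no new-or-worse rule is stated, so the counts can include old bleeds and omit late-found ones

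*Combined protocol and SAP*

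**What the plan says.** - **First scan.** Section 4.1.2, Note 1, requires it either before the drug starts or "within 4 hours of initiation of study drug". Only a known bleed excludes an infant (4.1.2). The cranial ultrasound paragraph of 4.2.5 bars randomization after a positive scan, but only for a scan done before the drug starts.
- **Second scan.** Section 4.2.5: "A second cranial ultrasound is obtained preferably within 24 hours (maximum within 96 hours) of completion of the study drug".
- **Event window.** Section 4.2: "The monitoring period is defined as the period of study drug infusion and the first 24-hours following study drug cessation". Section 5.5.1 sets the same limit for adverse-event reporting and justifies it by milrinone half-lives.
- **DSMC rule.** Section 5.5.3(c), severe intracranial hemorrhage, applies "while on study drug therapy and within 24 hours of completion of study drug therapy". Item (d), life-threatening hemorrhage, states no window of its own.
- **What counts.** Section 5.5.2 lists "Abnormal cranial imaging consistent with intracranial bleed". Section 3.5 grades bleeds by their appearance on imaging. Neither place, nor 5.5.3, requires the finding to be new or worse than on the first scan.
- **Safety outcome.** Secondary outcome (x) in 3.2 names the incidence of intracranial bleeding, with no window.

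**The concern.** Section 3.5 relies on the first and repeat ultrasounds to monitor for bleeding, so for many infants the scan may be the only evidence of when a bleed arose. The counting rules do not fit that schedule at either end.

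At the start, baseline is the 30 minutes before the infusion (4.2), so a first scan at 0 to 4 h already falls in the monitoring period. A bleed seen there may predate the drug, yet it meets the adverse-event description. If the drug is then stopped, the reasons listed in 4.2.5 include a side effect, with intracranial hemorrhage named.

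At the end, a second scan at 24 to 96 h complies with the protocol, but its finding comes after reporting has closed.

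Intracranial bleeding is part of Specific Aim 2, a named safety outcome and one of the DSMC triggers. With 33 infants per arm, one bleed counted wrongly is visible in the result.

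**Working it through.** **1. The plan's own figure.** The timing rules have no stated figure. The nearest is Table 8 in 5.1: an observed rate of 0.06 with n = 33 has 95% CI (0.007, 0.2). The Clopper-Pearson interval for 2/33 is (0.0074, 0.2023), so it reproduces. The lowest rate in that table is therefore two infants. One infant is 1/33 = 3.0 points, so one bleed wrongly added or dropped turns 2/33 (6.1%) into 3/33 (9.1%) or 1/33 (3.0%).

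**2. The windows.** The maximum infusion is 72 h (4.2.5).
- Event window closes at the latest: 72 + 24 = 96 h after drug start.
- Second scan permitted until: 72 + 96 = 168 h after drug start.
- Permitted second-scan time outside the event window: 96 - 24 = 72 h, and 72/96 = 75%.
- Permitted first-scan time inside the event window: up to 4 h.

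The 75% is a share of permitted time, not of scans.

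**3. Comparison with other harms in 3.5.** The blood-pressure and inotrope-score criteria for hypotension are judged against the pre-drug or baseline value. Renal dysfunction must be new-onset, and its creatinine-rise criteria use the same reference. Intracranial bleeding has no such comparator.

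**4. Direction and possible size (assumed rates).** Let q be the share of infants with an unrecognized prior bleed, f the share of first scans done after drug start, p the true new-bleed rate, all found only on the second scan, and g the share of second scans done after 24 h. If events are dated by the scan,

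observed rate = qf + (1 - qf) × p × (1 - g).

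The documents give none of q, f, p or g. Per arm of 33:
- Old bleeds counted, 33qf: 33 × 0.03 × 0.25 = 0.25, up to 33 × 0.10 × 1.0 = 3.3.
- New bleeds omitted, 33pg: 33 × 0.06 × 0.25 = 0.5, up to 33 × 0.21 × 0.75 = 5.2.

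The two errors act differently. Take true rates of 6% v 21% (difference 15 points, ratio 3.5):
- Old bleeds only (qf = 0.06 × 0.5 = 0.03, g = 0): 0.03 + 0.97 × 0.06 = 8.8% v 0.03 + 0.97 × 0.21 = 23.4%. The difference is 14.6 points, almost unchanged; the ratio falls to about 2.6.
- Late omissions only (qf = 0, g = 0.5): 3.0% v 10.5%. The ratio stays at 3.5; the difference halves to 7.5 points.
- Both together:

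| True rates | q, f, g | Observed rates | Difference (points) | Ratio |
|---|---|---|---|---|
| 6% v 21% | 0.06, 0.5, 0.5 | 5.9% v 13.2% | 7.3 (true 15) | 2.23 |
| 6% v 21% | 0.06, 1, 0.75 | 7.4% v 10.9% | 3.5 (true 15) | 1.48 |
| 3% v 12% | 0.06, 0.5, 0.5 | 4.5% v 8.8% | 4.4 (true 9) | 1.98 |
| 3% v 12% | 0.06, 1, 0.75 | 6.7% v 8.8% | 2.1 (true 9) | 1.32 |

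These rows show direction and a range. They are not estimates for this trial.

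**The case against.** - **Onset or detection.** No section says that a bleed is dated by the scan. Item (c) can be read as referring to onset, and then a late scan could still report an in-window bleed. This stands as a limit on the claim. But two scans often cannot supply an onset date, and an adverse event described as an imaging finding points toward dating by the scan.
- **Only some infants.** The problem needs a post-start first scan or a second scan after 24 h, and within 24 h is the preferred timing. This stands.
- **Existing filters.** The DSMC trigger counts only events judged at least possibly due to the study drug, which may remove some old bleeds, though case by case. Outcome (x) has no window, so late-found bleeds may still be counted there. Item (d) has none of its own, although a preceding sentence in 5.5.3 may imply 24 h. The MOP holds the toxicity table, was not available, and may contain a baseline rule.
- **Size.** A reader might infer that the safety signal is roughly halved: with 5% prior bleeds, true rates of 12% v 3% (ratio 4.0) would appear as 17% v 8% (ratio 2.1). The documents support none of those rates, and the figure needs every first scan to follow drug start. If half do, the ratio is 14.5/5.5 = 2.6; if a quarter do, 13.25/4.25 = 3.1. The difference is 9 points throughout. Old bleeds also move rates toward the 20% DSMC threshold, not away from it.
- **DSMC effect.** At 33 enrolled, 12% v 3% is about 2/17 v 0/16 (Fisher p = 0.49), so no changed DSMC decision has been shown.
- **Cost of a longer window.** The 24 h limit has a pharmacological reason: 24/4.1 = 5.9 half-lives, using Table 4. A later limit admits bleeds after open-label milrinone, which either arm may receive. This stands, and is why late-found bleeds should be shown separately. But drug clearance does not determine when a scan detects a bleed.

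**Conclusion.** The mismatch holds in a limited form. If bleeds are dated by the scan that shows them, adverse-event reporting and DSMC item (c) can include bleeds that predate the drug and can omit bleeds first seen on a compliant second scan at 24 to 96 h. The gap is 72 of the 96 permitted hours. Its effect on the results cannot be computed from the documents.

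A reader might conclude that the intracranial-bleed outcome does count old bleeds and does drop new ones. The text does not support that: it depends on actual scan times, on the unstated dating rule and on what the MOP says, and outcome (x) states no window.

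With randomization and masking, prior bleeds should be similar in the two arms on average. The expected error is a muted safety contrast, not a false one.

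**What to change.** No scan is moved or added.

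1. In 5.4 and 5.5, count as an incident event a severe or life-threatening bleed that is new or worse than on the first scan, on any scan through the protocol-mandated second scan.
2. List first-scan bleeds separately by arm, split into scans before drug start and scans 0 to 4 h after it. Add a sensitivity analysis that counts the 0 to 4 h bleeds as events.
3. For intracranial bleeds, reconcile 5.5.1 and 5.5.3(c) with the second-scan limit in 4.2.5, and state a window for 5.5.3(d).
4. Show bleeds first detected within 24 h and at 24 to 96 h separately, noting any open-label milrinone or ECMO before the scan.

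Under (1) and (3), the permitted second-scan time outside the window falls from 72 h to 0, and the longest window from drug start goes from 96 h to 168 h. Sample size and power do not change.

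The cost is definition wording and some data handling: 4.2.5 records open-label milrinone for only 24 h after the drug stops, so that item would need to run to the second scan. Window length will vary between infants, some late bleeds may follow open-label milrinone, and a true bleed in the first 4 h may be classed as pre-existing. The separate displays in (2) and (4) make these visible.
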